- If the signed consent is provided as an electronic copy (dropped off at their place of residence) emailed ,photo/scanned to text, or faxed), the participant or LAR must return the original signed document on their first in person visit or by mail if there is no in person visit.
- If the signed consent form is mailed to the consent designee by the participant or LAR, The IRB-approved consent designee will sign their copy which they possess after the participant has acknowledged signature on their copy. Once the participants original copy is received the consent designee copies will be attached to make a single document.
- If the participant signed consent form is provided immediately by electronic format (emailed, faxed or photo/scanned to text, once received, the IRB-approved consent designee signs, dates/times this informed consent document.

We will provide participants with password protected ZOOM links for all meetings.

We will distribute flyers to the Maryland AARP, senior housing residents, African American hair salons, and on Facebook local group and organization sites. A study team member will obtain necessary permission from administrative staff at all locations before any flyers are distributed via postal mail or email.

We will randomize participants to each group with the following process. 1) Once we find potentially interested participants through the above referral sources, we will telephone screen for eligibility and explain study procedures. 2) If eligible by phone, the research assistant will re-screen, re-explain the study, obtain consent (via DocuSign or hard copy ), and conduct the baseline data collection. 4) If participants qualify for the study after this visit, within 48 hours of the baseline interview, we will randomize using a computer-based assignment scheme and communicate the assignment to participants by letter. An employee of the Johns Hopkins Center of Innovative Care in Aging will be unblinded and will complete the randomization for the project. 5) The person assigned to randomize will inform the nurses of the participants' group (intervention or control). 7) The nurses will contact the participant within one week to schedule the first appointment.

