The wait list control group will have data collectors schedule a Zoom video visit with them. The same data will be collected for the intervention group. Participants in the wait list control group will not start the DAPPER intervention until the intervention group has completed the study. The wait list control group will receive monthly phone calls to confirm contact information.

**Data Collectors:** The data collectors have been trained to obtain baseline and outcome measures of each participant. The data collectors will collect baseline and outcome data and are responsible for teaching the participants how to collect saliva samples. The data collectors will call participants to schedule the first Zoom video call. The data collector will call/log on at the mutually agreed time. The data collector will complete the questionnaire booklet with the participant and complete the frailty phenotype measurements

with the participant. If the participants meets the criteria for frailty, pain, and depression, enrollment in the study will continue. Upon completion of the nurses' visits, the data collectors will schedule a final visit with participants.

**Research Nurses:** An RN is the appropriate professional to conduct the visits because of the training in assessment skills, and knowledge base in physiology, medications, and patient education in pain and depressive symptoms. The nurses have been trained on the protocol. The nurses will call the participants to schedule the first visit. The nurses will meet with participants via Zoom video calls during a mutually agreed upon time. The nurses will work with participants to set goals surrounding pain and depressive symptoms. The goals will be participant driven and documented by the nurse. The nurse will then work with the participant to identify strategies to work on three goals.

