#### **5. Study Statistics**

##### **Sample size calculation and analysis of aims**

**Sample size:** To calculate effect sizes for planning a definitive trial our sample size calculations were based on the need to pilot DAPPER for pain and depressive symptoms. We assume an attrition rate of 13% during the 16-week follow-up based on the CAPABLE trial. Based on these assumptions, an initial sample size of 64 participants (32 in the intervention group and 32 in wait list control) would yield 52 participants (25 intervention, 25 wait list control) after attrition. It is unlikely we will detect a significant difference between the groups due to small sample size and limited follow-up.

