##### **Analytic approach:**

For DAPPER, the outcomes will be improvement in pain, depressive symptoms, and communication with health care providers. A database will be created and stored on a password protected encrypted computer. Prior to conducting the analysis, the distribution of the data will be examined to determine if they meet the assumptions of the analytical model and to explore the pattern of missing data. The number of sessions attended will be computed as an indicator of acceptability. To test the effect of the intervention on outcomes (depressive symptoms, pain), generalized estimating equations will be used (GEE) with time, group, and the time x group interaction. We will not be sufficiently powered to detect a significant effect; interpretation of the results will be based on the effect size associated with the time by group interaction for each outcome. One advantage of GEE is it allows all participants' data to be included in the analysis, even those who do not complete the study, providing an intention-to-treat analysis. We will also conduct sensitivity analyses with completers only and compare the effect size to the ITT analysis to estimate the effect size when all participants adhere to the intervention.

Acceptability of the intervention will be examined in multiple ways. We will examine percentages of people who stayed in each arm of the study and conduct numerous descriptive correlational analyses of the

association between the intervention compliance and other variables. These analyses will quantify intervention implementation by demographic and participant health variables. Analyses that utilize the post-randomization data (e.g. treatment compliance) will be evaluated in supplementary analyses. We will distinguish non-compliance with intervention from attrition or loss to follow-up, i.e. missing data. We will also use the one-on-one qualitative interviews to examine acceptability of the intervention.

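### The completers-only analysis is labelled as the effect under full adherence, but in general it addresses attrition and should be reported as such

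*Combined protocol and SAP*

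**What the plan says.** Section 5 (Study Statistics), Analytic approach, fits a GEE model with time, group and their interaction. It calls this intention-to-treat because women who leave early still contribute data. The next sentence adds a sensitivity analysis restricted to completers, which the team will use to "compare the effect size to the ITT analysis to estimate the effect size when all participants adhere to the intervention".

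The text gives no formal definition of completers. On adherence, the same section says "The number of sessions attended will be computed as an indicator of acceptability", but sets no threshold among the eight nurse visits. Its next paragraph says "We will distinguish non-compliance with intervention from attrition or loss to follow-up, i.e. missing data", and sends compliance analyses to supplementary work without naming a method.

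On the main reading of the trial, the section says "interpretation of the results will be based on the effect size associated with the time by group interaction for each outcome". On the control arm, the DAPPER Protocol section says "Participants in the wait list control group will not start the DAPPER intervention until the intervention group has completed the study".

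**The concern.** Staying in the study and adhering to the intervention are different things, and the plan says so itself. An analysis of women who stayed is a check on missing data. Calling it the effect when everyone adheres gives it a meaning that needs further assumptions, and none are stated.

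The stake is interpretation. A gap between the completers-only and ITT results would be read as the gain from full adherence when it may be selection. Equally, the absence of a gap would be read as showing that non-adherence costs nothing. The sample size section says the pilot exists to supply effect sizes for a definitive trial, so a mislabelled effect size could enter that planning.

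**Working it through.** **The plan's own figure.** No figure supports the adherence claim. The nearest is the retained sample: "We assume an attrition rate of 13% during the 16-week follow-up based on the CAPABLE trial", with 64 women said to leave 52, given as 25 per arm. This does not reproduce: 64 x 0.87 = 55.68, or 27.84 per arm, and 25 + 25 = 50. That is a separate matter. Here it only means that precision is shown for both 25 and 28 per arm.

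**Reading the text.**
- *Study completers.* The preceding sentence supports this reading. The Abstract has all participants assessed at 12 and 24 weeks, so a woman who stops the visits can still give an outcome and count as a completer.
- *Visit completers.* The follow-up text under Acceptability Qualitative Interviews speaks of finishing the intervention, so this reading is possible. At 12 weeks the wait-list arm has had no visits, so only the intervention arm can be filtered.

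**Inputs for an illustration.** From the document: 13% loss (stated for 16 weeks, applied here to the 12-week outcome) and 25 per arm. Assumed:
- full-adherence effect d = 0.40 SD;
- a fraction p = 0.20 are would-be stoppers, who get no benefit;
- without treatment, stoppers would be 0.5 SD worse at week 12;
- stoppers are g SD worse at baseline;
- baseline to week-12 correlation r = 0.5.

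The estimate is the between-arm difference in change, which is the time-by-group interaction. With complete data, ITT = 0.80 x 0.40 = 0.32.

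**Study completers, 13% lost per arm.** If all lost women are stoppers, 7 of the remaining 87 per 100 are stoppers. The stopper share falls by 0.20 - 7/87 = 0.1195.

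| Who is lost | Formula | Estimate | Error against 0.40 |
|---|---|---|---|
| Unrelated to stopping | 0.80 x 0.40 | 0.32 | -0.08 |
| Stoppers, both arms | 0.40 x 80/87 | 0.368 | -0.03 |
| Stoppers, intervention arm only | 0.368 + 0.1195 x (0.5 - g) | 0.428 (g = 0), 0.398 (g = 0.25), 0.368 (g = 0.5) | +0.03, 0.00, -0.03 |
| Stoppers, wait-list arm only | 0.32 - 0.1195 x (0.5 - g) | 0.260 (g = 0), 0.290 (g = 0.25), 0.32 (g = 0.5) | -0.14, -0.11, -0.08 |

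In the first row the completers-only result equals ITT, so the comparison suggests that adherence makes no difference, although by construction it makes 0.08 SD.

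**Visit completers, intervention arm filtered only.** Estimate = 0.40 + 0.20 x (0.5 - g): 0.50, 0.45, 0.40 and 0.35 for g = 0, 0.25, 0.5 and 0.75. The errors are +0.10, +0.05, 0 and -0.05.

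**Precision.** The 95% half-width is 1.96 x sqrt(2(1 - r)) x sqrt(2/n). At r = 0.5 it is 0.55 for n = 25 and 0.52 for n = 28. For n = 25 it is 0.66 at r = 0.3 and 0.43 at r = 0.7.

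**Dependence on assumptions.** The 0.5 SD gap must be the untreated gap. If it were the observed gap in the treated arm, the untreated gap would be 0.5 - 0.4 = 0.1, and the visit-completer values become 0.42, 0.37, 0.32 and 0.27. A simulation with other assumptions (stoppers get half the effect; correlations of 0.5 between prognosis and outcome and, where selection operates, between prognosis and retention or adherence) gives 0.36 for ITT. Study completers give 0.30 to 0.42. Visit completers with follow-up data give 0.34 to 0.53. The target of 0.40 is recovered only for visit completers with no selection.

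**The case against.** The strongest reply is that completers is clear enough in context. The sentence before it concerns women who do not finish the study, so study completers are meant and the loss of the randomised comparison does not arise. That stands. A reader might infer that the plan intends a per-protocol analysis with one arm filtered. The document does not say so, and that branch is only a warning about the other reading. Completion could also be judged at 24 weeks, after the wait-list arm has been offered visits. Selection would then fall on both arms, and if equal it would give 0.40 under the assumptions above. The plan does not state this either.

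The second reply is that the plan already explores missing data, reports retention by arm and keeps compliance work supplementary. That also stands, and limits the consequence. It does not withdraw the full-adherence sentence.

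A reader might infer a large or consistently favourable bias. The documents give no adherence rate, no prognostic gap and no effect size, so neither the size nor the sign is known. A baseline table of completers and non-completers would not settle it. With 32 per arm, 13% loss is about 4 women and 20% stopping about 6. The 95% half-width for a baseline gap within an arm is then 1.96 x sqrt(1/4.16 + 1/27.84) = 1.03 SD, or 1.96 x sqrt(1/6.4 + 1/25.6) = 0.87 SD.

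**Conclusion.** The concern holds as a point about the label. The completers-only comparison does not in general estimate the effect under full adherence. On the natural reading it shows sensitivity to attrition, which the plan itself separates from non-compliance.

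Under the stated assumptions the error runs from about -0.14 to +0.10 SD and can be zero. Other assumptions move these limits. Either way it is small beside a 95% confidence interval of about +/-0.5 SD.

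Severity is minor. The analysis is secondary, and the main interpretation rests on the GEE interaction, which this point does not touch.

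**What to change.** In section 5, Analytic approach:

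1. State that completers are women who provided the 12-week outcome.
2. Delete the clause that presents the comparison with ITT as the effect when all participants adhere.
3. Report the analysis as sensitivity to attrition, so that its effect size is not used as a full-adherence effect when the definitive trial is planned.

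The cost is one definition and one reworded sentence. No new data or analyses are needed, and the planned session counts and supplementary compliance analyses can stay as they are.

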## 6. Risks

### a. Medical risks, listing all procedures, their major and minor risks and expected frequency.

Minimal risks to study participants are expected. There is a chance participants may experience some discomfort, or fatigue in completing saliva specimen collections. Participants may become fatigued or emotionally distressed while completing battery of questions. When performing the frailty phenotype walking speed tests participants may stumble, fall, or become short of breath or fatigued. If strategies include any type of physical activity (e.g. tai chi exercises) participants may become short of breath, fatigued, or may experience pulled muscles or dizziness.

### b. Steps taken to minimize the risks.

Participants can decline the saliva specimen collection or stop collecting specimens at any time. Participants can decline saliva collection or stop at any time. Participants can also decline to answer any of the survey questions. Research staff has been trained to interact with participants in a positive, non-judgmental manner that encourages honest communication and a partnership approach to study participation. Participants may decline the walking speed test, or any exercise strategies suggested by the nurse. The nurses have the necessary training to recognize respiratory distress and how to reduce falls (e.g. removal of clutter, assessing for dizziness and balance) via Zoom. The principal investigator will be made aware of any adverse reactions or events. Participants will receive a follow-up telephone call to assure that the reaction/event has resolved. If the reaction/event persists, a referral will be made to the participant's primary care provider for further evaluation.

Procedures for protecting against and minimizing potential risks:

If any physical problems emerge during any of the home visits, immediate medical attention will be sought for the participant. The risk of invasion of privacy will be addressed with participants during the informed consent process. All personnel involved in the study will be fully trained and certified in the protection of human subjects and HIPAA regulations. We will use a virtual video call software called Zoom. Zoom is encrypted, collects no protected health information (PHI) and any data transmitted during the call is destroyed when the call ends. It is both HIPAA and HITECH compliant.

This certification will be kept current throughout the study. As part of the informed consent process, participants will be notified of their rights pertaining to protected health information. Participants will be informed that they can stop the questionnaire and rest at any time. All study participants will be provided referral information to existing health services as in typical or usual care. Thus, participants have the information to access any services that they may perceive as necessary independent of their study participation.

The risk of breaching study participant confidentiality will be minimized by identifying all participants by code numbers, securing all data collected in locked files in the PI's office, and screening information to locked file cabinets with limited staff access. Pre-coded data collection instruments are prepared for use with study participants at each testing occasion. Identification numbers to assure subject confidentiality will be used. Only

one master log of subject names, addresses, telephone numbers, and study identification assignment will be maintained in a password protected computer program. Data collection will be on computer tablets that are password protected. Audio recording of nurse visits will be routinely conducted for fidelity and quality control review. These recordings will be identified by numbers only and stored in files on computers of the project coordinator and [name] who will provide fidelity oversight of the interventionists. Access to these computer files will be password protected; recordings will not contain respondent name or other personal identifying information and will not be transcribed. Recordings will be used only for quality control and training purposes and then destroyed (deleted from computers) within one year of trial completion.

**Plan for Data and Safety Monitoring:** This study is partially funded through the Older Americans Independent Center (OAIC) Pepper Center at Johns Hopkins University. Data and safety reports will be reviewed by the OAIC Director and/or co-PI. In the yearly progress report to NIH, the OAIC Directors will certify that the principal investigator has read all data and safety reports, in addition to making sure all corrective actions have been taken where there were concerns and/or that no concerns were noted.

**e.2 Verification of eligibility criteria:** The OAIC'S Data and Safety Monitoring Board reviews all applications for OAIC support that are being considered for funding. The board will verify that the inclusion and exclusion criteria are acceptable, or they will recommend revisions.

**e.3 Frequency of Data and Safety Monitoring:** Reports are reviewed quarterly, in conjunction with review of OAIC supported investigator progress reports. The OAIC DSMB is convened every 6 months. Unscheduled reviews may be conducted if necessary, at the request of the OAIC Director, study PI, SO/DSMB, or NIA program official.

**e.4 Content of Data and Safety Monitoring Reports:** Reports include, at a minimum, study status; descriptions of all SAEs, AEs, UPs, and protocol deviations (including enrollment of an ineligible participant); and any abnormal laboratory, imaging, and other test results. The study PI will attest his/her knowledge to the list of SAEs, AEs, UPs, and protocol deviations completed or that no SAEs, AEs, UPs, and protocol deviations occurred.

The members of the DSMB will be available to offer advice and provide ad hoc consultation throughout the study period. There will be continuous investigator monitoring with prompt incident reporting to the OAIC, Johns Hopkins Internal Review Board, Robert Wood Johnson Foundation, and National Institute of Health (NIH). Evaluation of this trial will include periodic assessments of data quality, participant recruitment, accrual, and retention. All adverse events will be reported to the IRB and the chair of the DSMB within 48 hours if attributable to the study. Members of the DSMB may request an interim analysis of data, which will be presented by the trial biostatistician in a session closed to the PI. The minutes meetings of the DSMB will be reported to Robert Wood Johnson Foundation, NIH, and IRB.

**Adverse Event (AE) Reporting:** The DSMB will be notified by the principal investigator of any serious AE within 48 hours of initial notification to the project team. All members of the DSMB will receive copies of all safety reports at the time of submission to the IRB. In addition, a listing of AEs and their attribution (e.g., level of probability of being study related, intervention related, or unrelated to study or treatment) will be provided to the DSMB on a monthly basis. We do not anticipate any adverse reactions to the intervention. Based on our previous work and studies in this area by others, there is only a small risk that participants will become increasingly anxious to the point that it becomes an adverse event (e.g., harmful to self or others) as a consequence of the activity intervention or having a member of the research team in their home. However, interviewers/interventionists are well trained to manage this reaction or make an effective referral if necessary.

Given that interviews for data collection and interventions via video, there is the potential for a member of our research team to encounter a potential emergency that is not related to study participation (e.g., dehydration, environmental risk, medical emergency). Following the emergence of the need to account for

such events in behavioral interventions differently than in medical/clinical studies, we refer to such events as “alerts” and have well-developed procedures for their management. All alerts will be reported to the DSMB on a biannual basis. However, the reporting of alerts to the IRB of JHU is not required (see Chart below of potential alert events and plan for their management and reporting).

**Recruitment, AE, and Alert Reports:** Reports presented to the DSMB will include data on enrollment (study accrual by month; comparison of expected to actual enrollment; number of individuals screened, number eligible and number ineligible, number randomized by gender, AEs, and alerts. In addition, the DSMB will receive reports of the number of study participants who discontinue from the treatment group and/or the study and reasons for discontinuation. We propose that reports are provided to the DSMB twice yearly. However, the DSMB will decide upon the schedule of reports. In addition, the DSMB may request reports as needed as well as the unblinding of the data should they deem this necessary. If unblinded efficacy data is required, the biostatistician for this study ([name]) will serve as a liaison between the PI, database, and the DSMB in order to assure that the PI and investigative team remains blinded.

Plan for reporting unanticipated problems or study deviations:

